The planned sample size is 120 subjects. Since this is the first multicenter study evaluating the effect of ATI-50002 Topical Solution in subjects with stable patchy alopecia areata, the sample size was based upon feasibility issue rather than on a formal power calculation. However, data from 120 subjects (40 per group), utilizing LOCF for missing data, provides 80% power to detect a 24-point difference in percent change from baseline in SALT score between any two treatment groups. This power computation was based upon the assumed standard deviation of 38%. Data from a previous study NCT02197455 showed that the standard deviation in percent change from baseline in the SALT score is 30.3%. The 38% standard deviation assumption used for this power computation was chosen to account for the increase in variance due to the lower baseline SALT entry criteria for this study as compared to NCT02197455.

Statistical Methods

The primary efficacy variable will be the percent change from baseline in the SALT score at Week 24 (Visit 10). This represents the percentage of hair regrowth. It will be calculated as the mean of the changes from baseline (Visit 2) SALT score to Week 24 (Visit 10) SALT score, divided by the baseline SALT score and expressed as a percentage. Missing data for the primary endpoint will be imputed using Last Observation Carried Forward (LOCF) methodology. The analysis will be conducted on the relative percent change from baseline over time including all visits using a mixed effect model repeated measures (MMRM). The adjusted mean (LS Mean) for percent change from baseline in the SALT score at each visit, estimated from the MMRM, with the estimated standard error and 95% confidence interval (CI), will be presented in tabular and graphic format. The difference in the adjusted means between treatment groups and the associated 95% CI of the difference will be provided. No adjustment for multiplicity will be made. The model will include fixed effect terms for treatment, study visit, baseline SALT score group (<50 , ≥ 50), and treatment by SALT group interaction. The primary analysis will be based on the Intent-to-Treat (ITT) population. Statistical significance for primary efficacy endpoint will be declared if at least one treatment group comparison at the Week 24 visit has a two-sided p-value less than or equal to 0.05.

Secondary Efficacy Analyses

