7.2. Subject Randomization

Prior to the start of the study, Aclaris Therapeutics, Inc. or a designated third party will generate a list of randomization numbers that shall be transmitted to the assigned clinical packaging organization for study medication labeling. The randomization list will be stored with access limited to designated personnel for study medication labeling. The randomization list will be made available, as appropriate, to unblind the database.

In the double-blind period, subjects will be assigned to 1 of the 3 treatment groups in a random manner and at a 1:1:1 ratio. At Baseline (Visit 2), an investigational center staff member will assign study medication to eligible subjects by selecting an appropriate Subject Kit. The staff member must select Subject Kits in chronological sequence and in an ascending numerical order starting with the lowest available Subject Kit number. No Subject Kit number may be omitted or reused. The Subject Kit number is the randomization number.

The investigational staff member randomizing the subject will enter the subject identifier, subject initials, and date randomized on both parts of the Subject Kit label, remove the tear-off part, attach it to the subject's study medication eCRF label page and record the Subject Kit number in the subject's eCRF.

In the open-label period, all subjects will receive the dosage strength of 0.46%.

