11.1. Sample Size and Power Calculations

The planned sample size is 120 subjects. Since this is the first multicenter study evaluating the effect of ATI-50002 Topical Solution in subjects with stable patchy alopecia areata, the sample size was based upon feasibility issues rather than on a formal power calculation. However, data from 120 subjects (40 per group), utilizing LOCF for missing data, provides 80% power to detect a 24-point difference in percent change from baseline in SALT score between any two treatment groups. This power computation was based upon the assumed standard deviation of 38%. Data from a previous study NCT02197455 showed that the standard deviation in percent change from baseline in the SALT score is 30.3%. The 38% standard deviation assumption used for this power computation was chosen to account for the increase in variance due to the lower baseline SALT entry criteria for this study as compared to NCT02197455.

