### **5.2.2. Primary Efficacy Analysis**

Descriptive statistics for the SALT score, change, and percent change from baseline will be presented for each scheduled analysis visit. Percent change from baseline in SALT over time up to Week 24 will be analyzed using a mixed effect for repeated measures (MMRM) model. This primary analysis will utilize the score with imputation for LOCF and will be based on the ITT population. The model will include fixed effect terms for treatment, study visit, baseline SALT score group (<50, >=50), and treatment by SALT group interaction. Within-subject variability will be modeled using a compound symmetry covariance structure. The least squares mean (LS Mean) percent change from baseline in the SALT score at each visit, estimated from the MMRM model, with the estimated standard error and 95% confidence interval (CI), will be presented in tabular and graphic format. The difference in the adjusted means between treatment groups and the associated 95% CI of the difference will be provided.

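### The primary model uses one residual variance for both baseline SALT groups, although the planning SD implies more variance at low SALT; if LS means are equally weighted and group sizes differ, its SE is miscalibrated

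*Protocol*

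**What the plan says.** The sample-size text (Protocol Synopsis and 11.1, repeated in SAP 3.1) states "This power computation was based upon the assumed standard deviation of 38" percent. A previous study, it says, "showed that the standard deviation in percent change from baseline in the SALT score is 30.3" percent, and the larger value was "chosen to account for the increase in variance due to the lower baseline SALT entry criteria for this study as compared to NCT02197455".

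The primary model (Protocol 11.4.1, SAP 5.2.2) has fixed effects for treatment, visit, baseline SALT group (<50, ≥50) and treatment by SALT group. Only the SAP addresses covariance: "Within-subject variability will be modeled using a compound symmetry covariance structure". Neither document provides for a variance that differs by SALT group, a robust standard error, or the weights given to the two SALT groups in the adjusted means. SAP section 5 names SAS 9.4 or higher as the software.

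On allocation, Protocol 7.2 says "subjects will be assigned to 1 of the 3 treatment groups in a random manner and at a 1:1:1 ratio". It does not mention stratification by SALT. The expected share of subjects below 50 is not given anywhere.

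SAP 5.2.7 repeats the primary analysis within each SALT group, so each of those fits has its own variance.

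**The concern.** The endpoint divides by baseline SALT, and entry runs from 15 to 95. A change of 10 SALT points is 67% of a baseline of 15 (10/15), 20% of 50 and 10.5% of 95. The same absolute change is therefore a far larger percentage at the low end, which fits the sponsor's reason for raising the SD.

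The model estimates a treatment difference in each SALT group, and the overall contrast combines the two. When one residual variance serves both groups, the noisier group's contribution is given too little uncertainty and the quieter group's too much. Whether these errors cancel depends on the weights and on the group sizes.

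The primary p-value and confidence interval are at stake. Success needs only one comparison with a "two-sided p-value less than or equal to 0.05", without multiplicity adjustment, so there is no slack to absorb a standard error that is too small.

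**Working it through.** **1. The plan's own figure.** Inputs: 40 per group, difference 24, SD 38, two-sided 0.05. The standard error is 38 × √(2/40) = 8.50, so 24/8.50 − 1.96 = 0.86 and power is 80.6% (79.7% with a t-test on 78 df). The stated 80% reproduces.

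**2. Standard error of the equal-weight contrast.** Let n1, n2 be the numbers per arm with SALT <50 and ≥50, s1, s2 their SDs, and N = n1 + n2. For the difference between two arms, averaged equally over the SALT groups:

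- true variance = ½ (s1²/n1 + s2²/n2)
- variance from the pooled model ≈ ½ s² (1/n1 + 1/n2), with s² = (n1 s1² + n2 s2²)/N
- ratio R = true/model = (n2 s1² + n1 s2²)/(n1 s1² + n2 s2²)

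If s1 and s2 differ, R = 1 only when n1 = n2. The two-sided type I error is 2[1 − Φ(1.96/√R)].

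**3. Weights from the observed split.** With weights n1/N and n2/N, true and model variance both equal 2(n1 s1² + n2 s2²)/N². R is then 1 at any split.

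**4. Assumed SDs.** The documents give no SD by group. Two cases are used, both with s2 = 30.3, the previous study's value:

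- Case A: overall within-group SD is 38, so s1² = [38² − (1 − p) × 30.3²]/p, where p is the share below 50.
- Case B (milder): s1 = 38.

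Example, case A at 30:70 (n1 = 12, n2 = 28): s1² = (1444 − 0.7 × 918.09)/0.3 = 2671, so s1 = 51.7. R = (28 × 2671 + 12 × 918)/(12 × 2671 + 28 × 918) = 1.486 and √R = 1.219. Since 1.96/1.219 = 1.608, the type I error is 10.8%.

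Example, case B at 30:70: R = (0.7 × 1444 + 0.3 × 918.09)/(0.3 × 1444 + 0.7 × 918.09) = 1.196, giving 7.3%.

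| Split (<50 : ≥50) | Case A: s1 | Case A: type I error | Case B: type I error |
|---|---|---|---|
| 30:70 | 51.7 | 10.8% | 7.3% |
| 40:60 | 47.3 | 7.1% | 6.1% |
| 50:50 | 44.4 | 5.0% | 5.0% |
| 60:40 | 42.4 | 3.7% | 4.0% |
| 70:30 | 40.9 | 2.8% | 3.2% |

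**5. Simulation.** Three arms of 40, with normal data, gave 11.1% (A) and 7.1% (B) at 30:70, and 2.6% and 3.2% at 70:30. Across splits from 25:75 to 75:25, a separate variance per SALT group gave 4.9–5.3%. One variance with observed-split weights gave 4.7–5.4%.

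**6. Repeated-measures check.** With complete data, compound symmetry and no treatment-by-visit term, the treatment contrast is an analysis of subject means, so R carries over if the SD ratio between groups is similar across visits. A small run (250 trials per split, six visits, within-subject correlation 0.7) gave true-to-model SE ratios of 1.15 at 13:27, 1.08 at 20:20 and 0.87 at 27:13. The formula gives about 1.17, 1.00 and 0.90. With 250 trials the Monte Carlo error is roughly 4–5%, so the run supports the direction but adds no precision.

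**The case against.** The sponsor can fairly say that miscalibration needs three things together: unequal group variances, unequal group sizes and equal-weight LS means. The documents state none of them. That stands, and the point is conditional for that reason.

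A reader might infer that the protocol itself contradicts equal variance across SALT groups. It does not go that far. Its sentence compares the overall SD of two studies with different entry criteria and says nothing about variance on either side of 50. Higher variance below 50 is a reasonable inference, not a stated fact.

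Part of the rise from 30.3 to 38 could also be a difference in means between the groups, which the SALT-group term would absorb. Protocol 2.1 does say that extensive hair loss has a poorer prognosis. Explaining the whole rise in this way at 50:50 would need a mean difference of √[(38² − 30.3²)/0.25] ≈ 46 points, so it is unlikely to account for all of it.

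Assigning 30.3 to the ≥50 group is an assumption, since the documents do not give the previous study's entry range. Case A also forces s1 up as the low-SALT group shrinks, which is why case B is shown beside it.

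The within-group analyses in SAP 5.2.7 would reveal a difference in precision, but they do not replace the primary test.

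**Conclusion.** The point holds in conditional form. The sponsor's rationale makes higher variance below SALT 50 likely, and the primary model makes no allowance for it. Under equal-weight LS means, calibration then depends on a split that nothing in the plan controls.

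For an s1 between 38 and the value implied by an overall SD of 38, with s2 = 30.3, the type I error is about 7–11% at 30:70, 6–7% at 40:60, 3.5–4% at 60:40 and about 3% at 70:30. These are assumed ranges, not estimates for this trial.

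Two stronger readings are not supported. One is that the primary p-value and interval are wrong unless the groups split evenly: with observed-split weights the standard error is about right at any split, and the documents do not say which weights apply. The other is that a definite amount of power is lost. The planned model has no treatment-by-visit term, so its treatment contrast averages over visits, and the SD of that average is not given. The 80% power statement itself reproduces and is not in question here.

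**What to change.** Before unblinding, in SAP 5.2.2 and Protocol 11.4.1:

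- let the covariance parameters differ by baseline SALT group (for example, the GROUP= option on the REPEATED statement), with Kenward-Roger or Satterthwaite degrees of freedom;
- state whether the LS means weight the SALT groups equally or by the observed split;
- apply both changes to the ALODEX percent-change analysis, which follows the primary method (Protocol 11.4.2, SAP 5.2.5).

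Separate variances keep the test close to 5% under either weighting. Specifying observed-split weights alone would also bring the overall standard error about right, but it changes which average effect is reported and should be chosen for that reason.

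The cost is one model option and a sentence or two of text. Compound symmetry needs two parameters per group, so four instead of two, and the degrees of freedom are slightly fewer.

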HIPAA	Health Insurance Portability and Accountability Act of 1996
HIV	Human Immunodeficiency Virus
H&E	Hematoxylin and Eosin
HLA-DR	Human Leukocyte Antigen- antigen D Related
ICAM-1	Intercellular Adhesion Molecule 1
ICF	Informed Consent Form
ICH	International Conference on Harmonization
i.e.	that is (Latin; id est)
IFN	Interferon
IHC	Immunohistochemical
IL	Interleukin
IUD	Intrauterine Device
IUS	Intrauterine Hormone Releasing System
ITT	Intent-to-Treat
IRB	Institutional Review Board
JAK	Janus Kinase
KER	Hair keratin panel
KRT	Hair Keratin
LDH	Lactate dehydrogenase
LDL	Low density lipoprotein
MedDRA	Medical Dictionary for Regulatory Activities
MHC	Major Histocompatibility Complex
mL	Milliliter
Mm	Millimeter
MMRM	Mixed Effect Model Repeated Measures
NCS	Not Clinically Significant
NK/ NKG	Natural Killer/ Natural Killer Group
NKG2D	A Transmembrane Protein
NMSC	Nonmelanoma Skin Cancer
OTC	Over-The-Counter
PDT	Photodynamic Therapy

Abbreviation	Term
PEG	Polyethylene glycol
PhGIC	Physician Global Impression of Change
PhGIS	Physicians Global Impression of Severity
PP	Per-protocol
PRO	Patient-Reported Outcome
PUVA	Psoralen and Ultraviolet A
SADBE	Squaric Acid Dibutyl Ester
SAE	Serious Adverse Event
SALT	Severity of Alopecia Tool
SCC	Squamous Cell Carcinoma
SGIC	Subject Global Impression of Change
SGIS	Subject Global Impression of Severity
SGITS	Subject Global Impression of Treatment Satisfaction
SI	Subject identifier
SN	Subject Number
SOP	Standard Operating Procedure
SR	Subject Rating
STAT	Signal Transducer and Activator of Transcription
T3, T4, TSH	Triiodothyronine, Thyroxine, Thyroid Stimulating Hormone
TIBC	Total Iron Binding Capacity
TEAE	Treatment Emergent Adverse Event
TNF	Tumor Necrosis Factor
Tyk2	Tyrosine Kinase 2
UPT	Urine Pregnancy Test
US	United States
UVA	Ultraviolet A
UVB	Ultraviolet B
WBC	White Blood Cell
WOCBP	Women of childbearing potential

2. INTRODUCTION

Aclaris Therapeutics, Inc. is developing ATI-50002 Topical Solution for the treatment of stable patchy alopecia areata. ATI-50002 is a potent highly selective inhibitor of Janus kinase 1 (JAK1) and Janus kinase 3 (JAK3).

2.1. Summary

Overview of Alopecia Areata

Alopecia areata (AA) is an autoimmune dermatologic condition, which, in its mildest form, is typically characterized by patchy non-scarring hair loss on the scalp and/or body. More severe forms of AA include total scalp hair loss, known as alopecia totalis (AT), and total loss of all the hair on the scalp and body- importantly, including loss of eyebrows, eyelashes, and intranasal hair-known as alopecia universalis (AU). While spontaneous regrowth of hair is common in the milder form of AA (patchy), where the hair loss may wax and wane, in patients with the extensive hair loss of AT or AU, spontaneous hair regrowth is rare. AA affects both males and females across all ethnic groups, with a lifetime risk of 1.7% (Safavi 1995). About two-thirds of affected individuals are 30 years old or younger at the time of disease onset.

The course of AA is unpredictable and while up to 50% of patients may recover within 1 year even without treatment, most patients will have more than one episode of hair loss (Price 2008). Factors portending a poorer prognosis for regrowth are more extensive hair loss presentations (extensive AA, AT, AU), an ophiasis pattern of hair loss, a long duration of hair loss, a positive family history, the presence of other autoimmune diseases, nail involvement, and young age of first onset (Tosti 2006, Weise 1996). In children, the disease may have a tendency towards worsening with time even if the initial presentation was mild, and the progressively disfiguring nature of the disease can be psychologically devastating. AA is highly associated with numerous psychiatric comorbidities including adjustment disorders, anxiety disorders and depression in both children and adults, and an effective treatment for AT and AU, the more severe forms of the disease, represents a significant unmet medical need (Bilgic 2014, Ruiz-Doblado 2003, Alkhalifah 2010).

The clinical development of innovative therapies in AA has lagged far behind other autoimmune conditions and there are currently no evidence-based treatments for AA. A Cochrane database review highlighted that few therapies for AA have been comprehensively evaluated in randomized clinical trials and that no treatment has demonstrated significant benefit compared to placebo according to evidence-based assessments (Delamere, 2008). This lack of good evidence-based data remains a challenge for physicians attempting to select efficacious treatments for their patients and, as a result, numerous approaches to treatment exist and are typically based on considerations such as the age of the patient, the extent and/or duration of the disease, patient expectations, cost considerations (both time and financial resources) and physician preferences and experience.

Common treatments for the less severe (patchy) form of AA include corticosteroids, either topically applied or injected intralesionally into the alopecic areas, or the induction of an allergic reaction at the site of hair loss using a topical contact sensitizing agent- an approach known as topical immunotherapy- typically with the topical contact sensitizers diphenylcycloprophenone (DPCP), squaric acid dibutyl ester (SADBE), or treatment with topical anthralin. While these

same treatment options may be utilized for the more severe forms of AA, their use in the more severe forms of AA is limited not only due to limited efficacy, but also because of the impracticality of using them over extensive body surface areas. Additional treatments used for extensive forms of AA (AT, AU) have included systemic steroids (pulsed or chronically administered), immunosuppressive agents such as cyclosporine or methotrexate, phototherapy with psoralen +UVA (PUVA), narrow-band UVB, photodynamic therapy (PDT), laser therapy (e.g., excimer laser, fractional photothermolysis lasers), prostaglandin analogs, etanercept, bexarotene and others, all with varying degrees of success and each with its inherent risk of adverse effects and unproven efficacy (Alkhalifah 2010, Price 1999, Hordinsky 2015, Strober 2005). Most recently, however, a breakthrough in the understanding of the pathophysiology of AA and several case reports in the literature have suggested that a group of inhibitors of the JAK-STAT pathway, the Janus Kinase (JAK) inhibitors, or “jakinibs” may be efficacious in the treatment of AA even in its most severe phenotypes, AT and AU (Jabbari, 2015, Pieri, 2015, Xing 2014).

The JAKs are members of a family of tyrosine kinases that are involved in cytokine receptor signaling. The JAK family of enzymes (JAK1, JAK2, JAK3, Tyk2) plays an essential role in regulating the signaling process of most cytokines in cells by linking the cytokine-induced signaling from the cell surface membrane receptors to signal transducers and activators of transcription, or STATs, within the cells. Once these JAK receptors are activated by the binding of a cytokine to the appropriate receptor, they initiate a JAK-STAT signaling pathway which can modify gene expression and modulate important regulatory functions in the cell, including regulating immune and inflammatory responses. JAK1 and JAK3 are constitutively associated with the alpha chain and the common gamma chain (γc), respectively, of the receptors for interleukin-2 (IL2), interleukin-4 (IL-4), interleukin-7 (IL-7) interleukin-9 (IL-9), interleukin-15 (IL-15), and interleukin-21 (IL-21). When these cytokines bind to their respective receptors, JAK1 and JAK3 are activated and initiate a signaling cascade that drives key inflammatory events, including lymphocyte activation and proliferation. The JAK inhibitors can block the cytokine receptor signaling pathways, (in this instance JAK1 and JAK3) blocking JAK-STAT transcription activation, and can therefore modulate inflammatory or immune responses, which can be beneficial in a variety of disease states, particularly, as recently reported, AA (Xing 2014). In that report, pharmacologic inhibition of JAK kinase signaling (JAK-STAT signaling) was reported to promote hair growth in both genetic mouse models of alopecia and in human patients.

Immunopathology & Pathophysiology of AA

Alopecia areata (AA) results from an autoimmune attack on the hair follicles that results in growing anagen-phase terminal hairs being induced to prematurely enter the telogen-phase and then shed. In its most acute state, AA demonstrates a histopathologically characteristic white cell infiltrate- the so called “swarm of bees”- encircling the human hair follicle, though more chronic forms typically demonstrate a sparser infiltrate (Jabbari 2016, Whiting 2003). Though the exact autoantigens expressed in the perifollicular epithelium that allow these specific T-cells to infiltrate the normally immunologically privileged hair follicle have been previously unknown, the T-cells that home to the hair follicle have been demonstrated to consist of both CD4 and CD8 cells. Most recent studies have further characterized a specific subpopulation of activated NKG2D-bearing CD8+ T-cells as being prominent in the peribulbar infiltrate, and it is now currently felt that these CD8+NKG2D+ effector T-cells preferentially localize to dermal sheath cells aberrantly expressing high levels of major histocompatibility complex (MHC) molecules and NKG2D ligands.

Interferons, as key activators of the MHC locus and of the cellular immune response, appear to play a key role in eliminating the immunologic privilege of the hair follicle and in inducing and maintaining the pathologic inflammatory response in AA. This is also seen in the C3H-HeJ mouse model of AA, in which IFN- γ is required for pathogenesis, and in which administration of IFN- γ accelerates disease. (Gilhar 2005, Hirota 2003).

AA has been viewed as a Th1-driven disease and, consistent with a pathogenic cellular immune response, elevated Th1 cytokines/ chemokines (IFN-induced chemokines [IP-10/CXCL10]) are seen in the peripheral blood of AA patients and IFN-inducible gene signatures have been described in the skin of AA patients and may correlate with disease activity (Arca 2004, Barahmani 2009, Kuwano 2007). Additionally, transcriptional profiles in human AA patients have shown a Type I IFN response in lesional biopsies and Th1 skewing and elevated IFN response cytokines/chemokines in both the peripheral blood and in reviewed scalp biopsies (Jabbari 2015, Xing 2014, Jabbari 2016). The cellular source of IFN- γ is hypothesized to be the T-cells, as in the AA mouse model IFN-gamma producing CD8+NKG2D+ cells dominate the dermal HF infiltrate, and in human AA, IFN- γ producing cells were identified in 4 of 5 dermal crawl-out assays (Christiano 2016). Additionally, data implicate IL-15 in driving activation of IFN-producing CD8 T-cells (Xing 2014).

Thus, preclinical and preliminary clinical information, as discussed above, strongly suggests that the primary pathophysiologic mechanism in AA (including AT and AU) is a cytokine mediated (primarily through T-lymphocyte induced upregulation of IL-15 and IFN gamma) induction of and prolonged maintenance of the telogen stage of the hair cycle. Inhibitors of the JAK/STAT pathway, particularly JAK1 and JAK3, are known to downregulate the effects of both IFN-gamma (through the inhibition at JAK1), and IL-15 (through inhibition at both JAK1 and JAK 3), and several published case reports have demonstrated the potential for compounds that are JAK1/3 inhibitors to induce hair growth in patients with AA (Kim 2017, Craiglow 2014 and 2017, Gupta 2016, Scheinberg 2016). As ATI-50002 is a potent inhibitor at JAK 1 and JAK 3, it is strongly suggested that ATI-50002 may be effective in the treatment of AA.

Among patients with AA, patients with higher disease burdens are unlikely to have satisfactory outcomes with current therapies. Aclaris Therapeutics, Inc. is developing ATI-50002 as a topical treatment for stable patchy AA. Aclaris is also developing ATI-50001 for the treatment of alopecia universalis (AU) and alopecia totalis (AT). ATI-50001 is an oral prodrug that is rapidly converted presystemically to ATI-50002, a potent highly selective inhibitor of Janus kinase 1 (JAK1) and Janus kinase 3 (JAK3). This study will evaluate whether or not the topically applied JAK1/JAK3 inhibitor, ATI-50002, will attenuate both IL-15 and IFN-gamma signaling, thereby blocking re-activation of CD8+NKG2D+ memory T-cells, and aborting the cytotoxic T-cell inflammatory response underlying AA.

In a previous Phase 1 study in healthy volunteers, single ascending oral doses of ATI-50001 of 50 mg to 500 mg and multiple ascending doses of up to 400 mg BID were well-tolerated. There were no SAEs. All treatment emergent adverse events (TEAEs) were transient and mild in intensity with the exception of 4 TEAEs: facial bone fracture, headache (2), and catheter site pain, which were classified as moderate. The most frequently reported drug related TEAEs occurring in > 1% of subjects were abdominal pain (10%), flatulence (7%), diarrhea (6%) and headache (6%).

Three subjects showed mildly elevated ALT or AST concentrations, which in two subjects were considered not clinically significant. For the other subject, the mild ALT elevation was reported as a treatment emergent adverse event possibly related to the study drug. No clinically significant laboratory abnormalities were observed. There were no clinically significant findings from 12-lead ECGs or vital signs assessments.

ATI-50001 was not detected in plasma and there was a dose-related increase in plasma of the active metabolite ATI-50002. The half-life of ATI-50002, after 14 days of dosing, was approximately 9.0 hours. Systemic levels of ATI-50002, following oral doses of ATI-50001 in healthy volunteers transiently reduced pSTAT5 activity in *ex vivo* IL-2 stimulated lymphocytes, indicating inhibition of the JAK signaling pathway. Upon multiple dosing, pSTAT5 activity showed a more sustained inhibition during the dosing period.

Non-clinical studies conducted with oral administration of ATI-50001 and topical administration of ATI-50002 support the topical administration of ATI-50002.

